### 10.1.3 Per-Protocol Set

Not applicable.

### 10.1.4 Dose-determining analysis set

Not applicable.

### 10.1.5 Pharmacokinetic analysis set

The pharmacokinetic analysis set (PAS) for both HGG and LGG cohort consists of all patients who receive at least one (full or partial) dose of dabrafenib or trametinib and provide at least one evaluable pharmacokinetic (PK) blood sample.

The definition of an evaluable PK blood sample will be further specified in the SAP.

### 10.1.6.1 Evaluable set

The Evaluable Set (ES) consists of all evaluable patients in the FAS who have centrally confirmed measurable disease, positive *BRAF* V600 mutation, an adequate tumor assessment at baseline, and a follow-up tumor assessment at least 8 weeks after starting treatment (unless disease progression is observed before that time) or have discontinued for any reason. For the HGG cohort, the evaluable set also requires that the patient's tumor is centrally confirmed by histopathology to be HGG.

The evaluable set will be used for sensitivity analyses.

# 10.2 Patient demographics/other baseline characteristics

For each cohort, demographic and other baseline data including disease characteristics will be summarized descriptively by treatment group based on the FAS. Categorical data will be presented as frequencies and percentages. For continuous data, mean, standard deviation, median, 25th and 75th percentiles, minimum, and maximum will be presented.

Relevant medical histories and current medical at baseline will be summarized separately by system organ class and preferred term.

# 10.3 Treatments (study treatment, concomitant therapies, compliance)

The safety set will be used for the analyses below for each cohort. Categorical data will be summarized as frequencies and percentages. For continuous data, mean, standard deviation, median, 25th and 75th percentiles, minimum, and maximum will be presented.

For the dabrafenib plus trametinib combination in each cohort the duration of exposure in weeks to dabrafenib and trametinib as well as the dose intensity (computed as the ratio of actual cumulative dose received and actual duration of exposure) and the relative dose intensity (computed as the ratio of dose intensity and planned dose intensity) will be summarized separately for dabrafenib and trametinib by means of descriptive statistics using the safety set. The duration of exposure will also be presented for the study treatment of dabrafenib in combination with trametinib.

For the carboplatin with vincristine control arm in the LGG cohort duration of exposure will be analyzed similarly.

The number of patients with dose adjustments (reductions, interruption, or permanent discontinuation) and the reasons will be summarized by treatment group (with the individual drugs also summarized separately) and all dosing data will be listed.

Concomitant medications and significant non-drug therapies prior to and after the start of the study treatment will be listed and summarized according to the Anatomical Therapeutic Chemical (ATC) classification system by treatment group.

#### 10.4 Primary objective

#### **HGG Cohort:**

The primary objective of the HGG cohort is to evaluate the anti-tumor activity of dabrafenib in combination with trametinib, as measured by overall response rate (ORR) by central independent review assessment using RANO criteria.

#### **LGG Cohort:**

The primary objective of the HGG cohort is to compare the anti-tumor activity of dabrafenib in combination with trametinib versus carboplatin with vincristine, as measured by overall response rate (ORR) by independent review assessment using RANO criteria.

#### 10.4.1 Variable

For the HGG cohort, the primary variable used to evaluate the anti-tumor activity of dabrafenib in combination with trametinib is the overall response rate (ORR), defined as the proportion of patients with a best overall confirmed Complete Response (CR) or Partial Response (PR) as assessed per Response Assessment in Neuro-Oncology (RANO) criteria by the independent reviewer.

For the LGG cohort, the primary variable used to evaluate the anti-tumor activity of dabrafenib in combination with trametinib versus carboplatin with vincristine is the overall response rate (ORR), defined as the proportion of patients with a best overall confirmed Complete Response (CR) or Partial Response (PR) as assessed per Response Assessment in Neuro-Oncology (RANO) criteria by the independent reviewer.

#### 10.4.2 Statistical hypothesis, model, and method of analysis

The primary analysis in the HGG cohort will be performed on the FAS. Point estimate and the exact binomial confidence intervals (CIs) (Clopper and Pearson 1934) of ORR will be provided. The lower bound of the CIs will be used to provide evidence that the true ORR is greater than a certain specific response rate.

The 95% CI, via the lower limit, is used to establish the levels of response which are exceeded by taking the combination therapy according to a robust standard of evidence (i.e. one-sided alpha=0.025). For example, out of 40 patients who have been enrolled and have completed at least 32 weeks of treatment or have discontinued treatment earlier, if 14 responses (35%) are observed then the corresponding 95% CI will exclude 20% which is greater, than the typical standard of care response rate previously observed (Lashford 2002; Nicholson 2007; Ruggiero 2006; Warren 2012; Hummel 2013).

With respect to the HGG cohort, the study also aims to provide evidence that trametinib gives added value to the dabrafenib and trametinib combination over and above dabrafenib monotherapy treatment. Since a lower standard of evidence is usually required to show such added value the lower limit of an 80% CI is used to identify the response rates which will be exceeded by taking the combination therapy based on a reduced level of evidence (one-sided alpha of 0.1). For example, if 18 responses (45%) out of the 40 patients are observed then the lower bound of 80% CI will exclude 32%, which is the response rate of dabrafenib monotherapy

observed from the study [BFR116013, CDRB436A2102]. In addition, the 95% CI can also be used to provide more robust evidence of the added benefit of trametinib. For example, if 20 responses (50%) are observed, then the lower bound of 95% CI will also exclude 32%.

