## **Efficacy Results**

### **High Grade Glioma**

Of the 31 enrolled HGG patients, 10 (32%) had investigator confirmed responses (CR + PR) following dabrafenib monotherapy. Independent radiologic determination of RANO response identified 14 patients (45%) with confirmed responses (CR+PR). Median duration of treatment was 24 weeks, and median duration of response was 33 weeks. Independent histopathology revealed that 7 of the 31 patients (23%) had grade 1 or 2 gliomas in the submitted tumor specimen. Four additional patients did not have sufficient tissue submitted to make any determination of glioma grade. The therapy has been generally well tolerated and adverse events easily managed.

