# 3 Objectives and endpoints

Objectives and related endpoints are described in Table 3-1 below.

| Table 3-1 | Objectives and related endpoints |
|-----------|----------------------------------|
|-----------|----------------------------------|

| Objective   | Endpoint   | Analysis               |
|---|--|------------------------|
| Primary   |  | Refer to Section 10.4  |
| HGG Cohort:   |  |                        |
| Evaluate the anti-tumor activity of dabrafenib in combination with trametinib, as measured by overall response rate (ORR) by central independent assessment using the RANO criteria.                                    | ORR, proportion of patients with a best overall confirmed Complete Response (CR) or Partial Response (PR) by independent assessment per RANO criteria.     |                        |
| LGG Cohort:   |  |                        |
| Compare the anti-tumor activity of dabrafenib in combination with trametinib versus carboplatin with vincristine, as measured by overall response rate (ORR) by central independent assessment using the RANO criteria. | ORR, proportion of patients with a best overall confirmed Complete Response (CR) or Partial Response (PR) by blinded independent review per RANO criteria. |                        |
| Secondary   |  | Refer to Section 10.5. |
| HGG Cohort:   |  |                        |
| Evaluate ORR by investigator assessment   | 1. ORR by investigator assessment per RANO criteria  |                        |
| 2. Evaluate duration of response (DOR) by investigator and  | 2. DOR, calculated as the time from the date of the first  |                        |

- Evaluate duration of response (DOR) by investigator and central independent assessment
- 3. Evaluate progression free survival (PFS) by investigator and central independent assessment
- Evaluate time to response (TTR) by investigator and central independent assessment
- Evaluate clinical benefit rate (CBR) by investigator and central independent assessment
- 6. Evaluate overall survival (OS)
- Evaluate the safety and tolerability profile of dabrafenib in combination with trametinib in children and adolescents
- 8. Evaluate the palatability of dabrafenib oral suspension and trametinib oral solution
- Characterize the pharmacokinetics of dabrafenib, its metabolites and trametinib in the study population

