#### 10.8 Sample size calculation

#### 10.8.1 **HGG Cohort**

Based on the exact binomial distribution, approximately 40 patients will be enrolled if the study is not stopped for futility at the time of the interim analysis.

The exact 95% and 80% CIs for potential observed ORR for 40 patients are shown in Table 10-3.

The 95% CI, via the lower limit, is used to establish the levels of response which are exceeded by taking the combination therapy according to a robust standard of evidence (i.e. one-sided alpha=0.025).

Due to the uncertainties regarding the historical control data there is no specific "success" threshold level that we can apply that the lower limit should be greater than to give robust evidence that dabrafenib and trametinib combination therapy is better than historical control; however, the study sample size gives reasonable operating characteristics for an illustrative threshold historical level of 20%, which is higher than the range expected based on the information given in the literature (Section 1.1.3).

The study also aims to provide evidence that trametinib gives added value to the dabrafenib and trametinib combination over and above dabrafenib monotherapy treatment. Since a lower standard of evidence is usually required to show such added value, the lower limit of an 80% CI is used to identify the response rates which will be exceeded by taking the combination therapy based on a reduced level of evidence (one-sided alpha of 0.1). Again it is difficult to ascertain a definitive threshold for "success" for evaluation in these circumstances but the number of patients in this trial give reasonable operating characteristics for an illustrative threshold level of 32%, which is the response rate observed in dabrafenib monotherapy patients in the study [BRF116013, CDRB436A2102] although based on limited data. Note that the 95% CIs can also be used to provide more robust evidence of the benefit of trametinib by looking at the lower limit compared to possible levels of dabrafenib monotherapy response.

Table 10-3 Exact Binomial 95 and 80 percent Confidence Intervals Around Potential Observed ORRs for N=40

| Number of responders | Observed ORR (%) | 95% exact CI (%) | 80% exact CI (%) |
|----------------------|------------------|------------------|------------------|
| 12                   | 30.0             | 16.6, 46.5       | 20.5, 41.2       |
| 13                   | 32.5             | 18.6, 49.1       | 22.7, 43.8       |

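### The illustrative 32% benchmark for trametinib's added value in the HGG cohort is an investigator-assessed monotherapy rate set against centrally reviewed ORR, for which the monotherapy rate in the same patients is 45%

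*Protocol*

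**What the plan says.** The HGG primary endpoint is centrally reviewed. Section 10.4 states the objective "as measured by overall response rate (ORR) by central independent review assessment using RANO criteria", and Table 3-1 defines the endpoint as "ORR, proportion of patients with a best overall confirmed Complete Response (CR) or Partial Response (PR) by independent assessment per RANO criteria".

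Section 10.4.2 then gives a second aim for the cohort, to provide evidence that trametinib contributes beyond dabrafenib alone. The lower limit of the 80% CI of ORR (one-sided 0.1) is the tool, with the 95% CI (one-sided 0.025) as stronger evidence. The worked example is that with 18 of 40 responders "then the lower bound of 80% CI will exclude 32%, which is the response rate of dabrafenib monotherapy". With 20 of 40, the 95% CI also excludes 32%. Section 10.8.1 repeats the benchmark as an "illustrative threshold level of 32%, which is the response rate observed in dabrafenib monotherapy patients in the study". Table 10-5 and the Protocol summary are built on the same value.

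Section 1.2.1.2.1 reports two monotherapy rates for one group of patients. By investigator: "Of the 31 enrolled HGG patients, 10 (32%) had investigator confirmed responses (CR + PR) following dabrafenib monotherapy". By central review: "Independent radiologic determination of RANO response identified 14 patients (45%) with confirmed responses (CR+PR". The Protocol summary, under purpose and rationale, repeats 14 of 31 (45%) as the centrally reviewed figure. Two other places show the same split with smaller denominators: 6/19 (31.5%) by investigator in Section 2.1 and 10/22 (45%) by independent assessment in Section 2.6.

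**The concern.** Sections 10.4.2 and 10.8.1 describe 32% simply as the monotherapy response rate. They do not say that it comes from a different assessor than the endpoint it is compared with, nor that the matching rate is about 13 percentage points higher (45.2% − 32.3%). The lower of two available rates from the same patients has become the bar for the centrally assessed endpoint.

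The consequence shows in the protocol's own example. The result offered as evidence of added value at the 80% level, 18/40 = 45%, equals the centrally reviewed response rate on dabrafenib alone. A combination that performed exactly like monotherapy under central review could then be described as evidence that trametinib contributes.

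The amendment history may explain this: Amendment 3 moved the HGG primary endpoint from investigator to central review. That is context only; the mismatch is in the current text.

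**Working it through.** **Inputs**
- N = 40; interim look at 16 patients, with futility considered if fewer than 5 respond (Section 10.8.1).
- Benchmark 32%, with 80% and 95% exact limits (Section 10.4.2).
- Monotherapy HGG rates: investigator 10/31 = 32.3%; central 14/31 = 45.2% (Section 1.2.1.2.1).

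**Step 1: responder counts needed.** The exact (Clopper-Pearson) lower limit for x responders of n is the α/2 quantile of a Beta(x, n − x + 1) distribution, with α = 0.20 or 0.05. For n = 40:
- 80% CI: 17 gives 31.7% and 18 gives 34.1%, so 18 are needed to exclude 32%.
- 95% CI: 19 gives 31.5% and 20 gives 33.8%, so 20 are needed.

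These match Table 10-3 and the protocol's examples.

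**Step 2: reproduce Table 10-5.** With r the count needed and p the true ORR,

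P(futility not met and limit above benchmark) = Σ over x = 5 to 16 of C(16, x) p^x (1 − p)^(16 − x) × P(Bin(24, p) ≥ r − x).

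At p = 45% this gives 55.2% for r = 18 and 31.4% for r = 20. At p = 55% it gives 91.7% and 78.5%. All agree with the table, which is arithmetically correct for the benchmark it names.

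**Step 3: read the table as the case of no added effect.** If trametinib adds nothing, the true central ORR equals the true central monotherapy rate:

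| True central rate, with and without trametinib | 80% CI excludes 32% | 95% CI excludes 32% |
|---|---|---|
| 35% | 12.1% | 3.6% |
| 40% | 30.5% | 12.9% |
| 45% | 55.2% | 31.4% |
| 50% | 77.6% | 56.0% |

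The stated one-sided levels are 10% and 2.5%. If the true rate really were 32%, the exact chances would be 5.7% and 1.3%, so the excess comes from the benchmark and not from the interval method. Ignoring the futility look, which does not bind, moves the 45% row only to 56.1% and 31.6%.

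**Step 4: precision of the 45%.** The exact 95% CI for 14/31 is 27.3% to 64.0%. For 10/31 it is 16.7% to 51.4%.

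**Step 5: use 45% for central ORR.** The 80% lower limit is 43.7% at 22/40 and 46.1% at 23/40, so 23 are needed. The 95% lower limit is 43.3% at 24/40 and 45.8% at 25/40, so 25 are needed. Using 14/31 unrounded gives the same counts.

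| True central ORR | 80% CI excludes 45% | 95% CI excludes 45% |
|---|---|---|
| 45% | 7.7% | 2.0% |
| 50% | 21.5% | 7.7% |
| 55% | 43.9% | 21.4% |
| 60% | 68.8% | 44.0% |
| 65% | 87.6% | 69.5% |

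**The case against.** The strongest reply is that 32% is not a rule. Section 10.8.1 calls it illustrative and based on limited data, and says a definitive success threshold is hard to establish. It also lets the 95% limits be compared with other possible monotherapy rates. Added value is not an objective or endpoint in Table 3-1, and no decision depends on 32%: futility uses 25%, and both the standard-of-care comparison and the gate for HGG subgroup analyses use 20%. All of this stands. It limits the severity but does not remove the mismatch. The caveat concerns uncertainty, not the assessor; both rates come from the same 31 patients, so limited data is no reason to prefer the investigator figure for a central endpoint. The Protocol summary gives the 32% probabilities without the caveat.

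A second reply is that a like-for-like comparison already exists: Section 10.5 plans investigator-assessed HGG ORR with 95% and 80% CIs. That is correct, and it is where 32% belongs. The protocol does not make that link and applies 32% to the primary ORR.

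A third is that 45% is itself imprecise and not a clean comparator. The two rates differ by four patients, and the monotherapy patients were enrolled across parts of a study that included dose finding at several dose levels. This also stands: 45% should not be treated as a known constant. It does not rescue 32%, since a true central rate of 40% already gives 30.5% and 12.9%.

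Finally, this cannot be left to the SAP, because the protocol itself fixes the benchmark, the example counts and the table.

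**Conclusion.** The point holds as a mismatch of assessor between benchmark and endpoint, and no section of the protocol acknowledges or repairs it. At the central point estimate of 45% and with no contribution from trametinib, the illustrative threshold would be exceeded with probability 55.2% (80% CI) or 31.4% (95% CI). These figures assume that the true central monotherapy rate is 45% and that the two study populations are comparable. They vary widely across the interval for 14/31.

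A reader might infer that an ineffective add-on would pass a formal test more than half the time. The documents do not support that. No hypothesis is stated for added value, the figure above one half applies only to the 80% CI, and it is the value at an imprecise point estimate. A reader might also infer that the HGG primary conclusion is compromised. It is not: the estimate of central ORR, the 20% benchmark and the 25% futility criterion do not use 32%.

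What does need correcting is the claimed ability to show added value on the primary endpoint. At a true ORR of 55%, the stated probabilities above 90% (80% CI) and above 78% (95% CI) become about 44% and 21% against the matching benchmark. Severity: should-fix.

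**What to change.** In Sections 10.4.2 and 10.8.1, Table 10-5 and the Protocol summary:
- Label 32% as investigator-assessed (10/31) and use it only against investigator-assessed ORR, whose 80% CI is already planned in Section 10.5.
- For centrally reviewed ORR, use the central monotherapy rate of 45% (14/31), state its exact 95% CI of about 27% to 64%, and keep the label illustrative.
- Restate the example counts for central ORR as 23/40 (80% CI) and 25/40 (95% CI).
- Recompute Table 10-5 against 45%. Replace the probabilities for excluding 32% at a true ORR of 55% with about 44% and 21%. The statement that the 95% CI excludes 20% with probability above 90% stays.
- Revise the Section 10.8.1 sentence that 40 patients give acceptable operating characteristics for the added-value comparison.

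The cost is wording, two example counts and one recalculated table, with no extra patients or assessments. The real downside is a less favourable stated chance of showing added value: against 45%, the 80% criterion reaches 87.6% only at a true ORR of 65%. The sponsor may therefore have to state the added-value aim for central ORR more cautiously.

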#### **LGG Cohort**

The primary efficacy analysis in the LGG cohort is the comparison of ORR based on independent review assessment between the two treatment arms. The following statistical hypothesis will be tested:

$$H_{01}$$
:  $ORR_t \leq ORR_c$  vs.  $H_{A1}$ :  $ORR_t > ORR_c$ 

where  $ORR_t$  is the ORR in the Trametinib plus Dabrafenib arm and  $ORR_c$  is the ORR in the carboplatin with vincristine arm. The analysis to test these hypotheses and compare the two treatment groups will consist of a Mantel Haenszel chi-square test at one-sided 2.5% level of significance.

The primary efficacy analysis will be performed on the FAS.

ORR will be summarized using descriptive statistics (N, %) by treatment arm along with two-sided exact binomial 95% CIs (Clopper and Pearson 1934).

#### 10.4.3 Handling of missing values/censoring/discontinuations

Patients with unknown or missing best overall response (BOR) will be counted as failures. If there is no baseline tumor assessment, all post-baseline overall lesion responses are expected to be 'Unknown'. If no valid post-baseline tumor assessments are available, the best overall response must be "Unknown" unless progression is reported. For the computation of ORR, these patients will be included in the FAS and will be counted as 'failures'.

### 10.4.4 Supportive and sensitivity analyses

The following supportive and sensitivity analyses will be performed for the HGG and LGG cohorts as appropriate.

The primary analysis on the FAS will be repeated on the evaluable set. The analyses of ORR, DOR, and PFS will be repeated based on radiological response assessed by independent review by only incorporating the radiographic data in the FAS. In addition, ORR, DOR and PFS will be evaluated using a ITT approach i.e including all response assessments irrespective of new anti-neoplastic therapy using the FAS.

If the primary efficacy analysis shows that the 95% CI of ORR excludes 20% for HGG and statistically significant for LGG, the following subgroups may be considered:

The primary efficacy endpoint ORR and secondary endpoint DOR by investigator and central independent assessments may be summarized by risk categories such as that determined by methylation analysis based on FAS and Evaluable set. The risk categories will be specified in a later SAP amendment prior to database lock

The SAP will pre-specify analyses that will be conducted using crossover data, if applicable.

Additional supportive analyses may be conducted to support the primary objective of the HGG and LGG cohorts if appropriate, and the details of these analyses will be defined in the SAP.

#### 10.5 Secondary objectives

#### **HGG Cohort**

With respect to the HGG cohort, the secondary objectives are to evaluate the overall response rate (ORR) by investigator assessment, duration of response (DOR), time to response (TTR), clinical benefit rate (CBR), progression-free survival (PFS) by both investigator assessment and central independent assessment, as well as overall survival (OS), and safety.

